3 ABBREVIATIONS

ADR	Adverse Drug Reaction
AE	Adverse Event
allo-HSCT	Allogeneic Hematopoietic Stem Cell Transplantation
ATS	American Thoracic Society
AUC	Area Under the Curve
Bid	Bis in die , twice daily
BO	Bronchiolitis Obliterans
BOS	Bronchiolitis Obliterans Syndrome
BDRM	Blind Data Review Meeting
CGI	Clinical Global Impressions
CGvHD	Chronic Graft Versus Host Disease
C _{max}	Maximum concentration
CRO	Contract Research Organization
CsA	Cyclosporine A
CsA-PG	Cyclosporine A Propylene Glycol
CSR	Clinical Study Report
DI	Deciliter
DLT	Double Lung Transplantation
DMC	Data Monitoring Committee
EC	Ethics Committee
eCRF	Electronic Case Report Form
EoS	End of Study
EoT	End of Treatment
ERS	European Respiratory Society
EU	European Union
EXP	Expiration date
FAS	Full Analysis Set
FEF ₂₅₋₇₅	Forced Midexpiratory Flow
FEV ₁	Forced Expiratory Volume in One Second
FVC	Forced Vital Capacity
GCP	Good Clinical Practice
HSCT	Hematopoietic Stem Cell Transplantation
IB	Investigator's Brochure
ICF	Informed Consent Form
ICH	International Council for Harmonisation of Technical Requirements for Pharmaceuticals for Human Use
IMP	Investigational Medicinal Product (L-CsA)

ISF	Investigator Site File
Kg	Kilogram
L	Liter
L-CsA	Liposomal Cyclosporine A
L-CsA CCI	[REDACTED] Nebulizer System
NHANESIII	Third National Health And Nutrition Examination Survey
MedDRA	Medical Dictionary for Regulatory Activities
Mg	Milligram
µm	Micrometer
mL	Milliliter
MMRM	Mixed Model for Repeated Measures
mOsmol	Milli Osmoles of solute per litre of solution
N (n)	Number of patients
PCR	Polymerase Chain Reaction
PG	Propylene Glycol
Ph Eur	European Pharmacopeia
PI	Polydispersity Index
PK	Pharmacokinetics
PPS	Per Protocol Set
PT	Preferred Term
Q1	Lower Quartile
Q3	Upper Quartile
SAE	Serious Adverse Event
SAP	Statistical Analysis Plan
SAF	Safety Analysis Set
SLT	Single Lung Transplantation
SmPC	Summary of Product Characteristics
SoC	Standard of Care
SOC	System Organ Class
SUSAR	Suspected Unexpected Serious Adverse Reaction
t _{max}	Time to reach the maximum concentration
ULN	Upper Limit of Normal
US	United States
USP	United States Pharmacopeia

4 PROTOCOL SYNOPSIS

Protocol Title:	BOSTON-4: A Phase IIa Multi-Center, Randomized, Single-Blind Safety and Tolerability Study of inhaled Liposomal Cyclosporine A in Bronchiolitis Obliterans Syndrome Following Allogeneic Hematopoietic Stem Cell Transplantation
Sponsor:	Zambon SpA [name], [name] Italy
Protocol Number:	BT – L-CsA – 201 – SCT (BOSTON-4)
EUDRACT Number:	2019-000718-13
IND Number:	78,854
Investigational Medicinal Product:	Liposomal Cyclosporine A (L-CsA) Inhalation Solution 10 mg twice daily (bid) or Liposomal Cyclosporine A L-CsA Inhalation Solution 5 mg twice daily (bid) or Liposomal Placebo (0 mg L-CsA) Inhalation Solution twice daily (bid)
Protocol Phase:	Phase IIa
Protocol Date:	Version 5.0; 30 April 2021
Protocol Amendment	4
Clinical Trial Centers/Countries:	Up to 20 centers in Europe.
Planned Clinical Trial Period:	Duration of therapy: 12 weeks Total clinical trial duration per patient: up to 18 weeks
Planned Number of Patients:	24 patients randomized Randomization: 1:1:1 Patients will receive investigational treatment or placebo via the L-CsA specific [REDACTED] Nebulizer System (L-CsA [REDACTED CCI]), in addition to standard of care (SoC) therapy.

	Treatment A: L-CsA 10 mg bid plus SoC (n=8) Treatment B: L-CsA 5 mg bid plus SoC (n=8) Treatment C: L-CsA 0 mg (placebo) bid plus SoC (n=8)
Objective:	The objectives of this study are to assess the tolerability, safety, pharmacokinetics (PK), exploratory efficacy and quality of life of two doses of aerosolized L-CsA vs placebo in addition to SoC therapy for the treatment of BOS in adult allogeneic hematopoietic stem cell transplantation (allo-HSCT) recipients.
Clinical Trial Design:	Phase IIa prospective, multi-center, single-blind, randomized clinical trial assessing two doses of inhaled L-CsA and placebo.
Eligibility Criteria:	Inclusion Criteria: 
1. Age \geq 18 years2. Patients must have undergone hematopoietic stem cell transplantation and have documented diagnosis of chronic Graft versus Host Disease (cGvHD), guided by the NIH consensus criteria.3. Patients must have been diagnosed with BOS within >6 months and ≤ 3 years at Screening visit.4. Spirometry test carried out at Screening visit must show:
• A FEV₁ above 51% of predictedAND• A $\geq 10\%$ decline in FEV₁ (L) within 2 years5. Patient must be capable of understanding the purposes and risks of the study, has given written informed consent, and agrees to comply with the study requirements.6. Women of childbearing potential must have a negative serum or urine pregnancy test within 7 days prior to randomization and must agree to use one of the methods of contraception listed in Appendix II through their End of Study Visit.
	Exclusion Criteria: 
1. Other acute or chronic restrictive or obstructive lung diseases, including but not limited to: active asthma (variable and recurring symptoms of airflow obstruction (reversible to beta-2 agonists) and bronchial hyper-responsiveness), chronic obstructive pulmonary disease, interstitial lung disease, or cryptogenic organizing pneumonia , neuromuscular weakness or diaphragmatic paralysis.2. Any acute pulmonary bacterial, viral (as confirmed by multiplex PCR) or fungal infection not successfully resolved at least 4 weeks prior to the Screening Visit.

	
3. Chronic renal dysfunction with serum creatinine ≥ 2.5 mg/dL.4. Chronic hepatic dysfunction with serum total bilirubin > 5x upper limit of normal (ULN), transaminases > 5x ULN, or alkaline phosphatase > 5x ULN.5. Evidence of clinical relapse of the primary malignancy, according to investigator's judgement, which warranted allogeneic bone marrow transplant.6. Use of azithromycin within 4 weeks prior to Randomization (Visit 1).7. Chronic oxygen use or use of non-invasive ventilation.8. Active smokers (i.e. any kind of inhaled nicotine consumption).9. Pregnant women or women who are unwilling to use appropriate birth control to avoid pregnancy over the course of the clinical trial (for details see Appendix II).10. Women who are currently breastfeeding.11. Known hypersensitivity to L-CsA or to cyclosporine A.12. Patients with life-expectancy of less than 6 months.13. Receipt of an investigational drug as part of a clinical trial within 4 weeks prior to the Screening Visit. Participation in registries, is allowed.14. Psychiatric disorders or altered mental status precluding understanding of the informed consent process and/or completion of the necessary procedures.15. Any co-existing medical condition that in the Investigator's judgment will substantially increase the risk associated with the patient's participation in the clinical trial.16. Pre-scheduled hospitalizations, surgeries or interventions planned to be performed after obtaining Informed Consent for this study.
Investigational Medical Product:	The L-CsA/Liposomal Placebo is supplied in glass vials containing 10 mg or 5 mg of L-CsA or 0 mg L-CsA. The 10 mg L-CsA or placebo lyophilisate is reconstituted with 2.4 mL 0.25% NaCl and the 5mg L-CsA lyophilisate is reconstituted with 1.2 ml 0.25% NaCl to obtain a ready to use dispersion for inhalation via the L-CsA CCI .
Mode of Administration/ Dosing Schedule:	The investigational medicinal product (IMP) will be administered bid by inhalation (morning/evening). At every visit, one dose administered via inhalation will be monitored by the clinical trial center personnel. Nebulization time per inhalation dose is approximately 5-10 minutes for the 5 mg dose and 8-13 minutes for the 0 and 10 mg doses.
Treatment Regimen:	Regardless of treatment allocation, all participants will continue to receive their SoC regimen as prescribed by their treating physician. Patients will be randomized to one of the following treatment groups: Treatment A (L-CsA 10 mg treatment plus SoC): L-CsA 10 mg/2.5 mL bid for a maximum of 12 weeks plus

	
SoC therapy
 
Treatment B (L-CsA 5 mg treatment plus SoC): L-CsA 5 mg/1.25 mL bid for a maximum of 12 weeks plus SoC therapy
 
Treatment C (0 mg L-CsA (placebo) plus SoC): L-CsA 0 mg/2.5 mL bid for a maximum of 12 weeks plus SoC therapy

Endpoints:	
Primary assessment: IMP tolerability and safety during the first 4 weeks of treatment
 
Secondary assessments:
 
• IMP tolerability and safety during the first 12 weeks of treatment;• CsA PK 
Exploratory efficacy assessments:
 
• FEV₁ % predicted at randomization compared to Week 2, Week 4, Week 8, and Week 12• FEV₁/FVC at randomization compared to Week 2, Week 4, Week 8, and Week 12• SF-36 Quality of Life Questionnaire at Baseline, Week 2, Week 4, Week 8, and Week 12 visits• Changes in the dose of corticosteroids and immunosuppressive therapy administered throughout trial duration 
IMP Tolerability Parameters:
 
• Local Tolerability:
○ Cough○ Wheezing○ Bronchospasm○ Throat irritation○ Change in FEV₁• Overall Tolerability:
○ Clinical Global Impressions (CGI) scale (on-site only)○ Investigator's tolerability assessment at Visit 3 and Visit 5 
Safety Parameters:
 
• Adverse events (AEs)• Serious adverse events (SAEs)• Clinical laboratory values• Vital signs• Physical Examination

	
Pharmacokinetic Parameters:
 
• PK: (Week 0) at pre-dose; directly after end of inhalation; 15, 30, and 45 minutes, and 1, 1.5, 2, and 4 hours after end of inhalation:
○ C_{max}○ t_{max}○ AUC_{0-4h}• Whole blood trough levels (at Weeks 2, 4, 8, and 12)
Assessments	
Clinical Trial Plan:
 
At total of 7 visits (Screening, Randomization (Week 0), Week 2, Week 4, Week 8, Week 12 (End of Treatment [EoT]) and Week 14 (End of Study [EoS]) will be performed during the clinical trial. AEs and concomitant medications will be recorded at all visits.
 
Screening: After informed consent has been obtained. Screening Visit procedures will be carried out to check general eligibility for participation up to 4 weeks prior to randomization. Blood will be drawn for safety profiles.
 
Visit 1, Week 0 (Baseline Visit, Randomization): Blood for baseline measures will be collected. Spirometry will be performed. A pregnancy test will be performed for all females of childbearing potential prior to randomization. A physical exam, including vital signs, will be performed. The CGI Questionnaire will be administered. The SF-36 Quality of Life Questionnaire will be administered. Patients will be randomized to study treatment and instructed on use of the L-CsA CCI. The first dose of IMP will be administered under observation and safety will be monitored. Spirometry will be repeated 1 hour \pm 20 min after completion of the first dose of IMP. Blood will be drawn for safety profiles and PK data at pre-dose. PK samples will be obtained directly after end of first inhalation, at 15, 30, and 45 minutes, and 1, 1.5, 2, and 4 hours after end of inhalation. If no tolerability issues are observed, patients will be permitted to leave the clinic. Patients will receive the full IMP supply for the 12 weeks treatment period. The second dose of IMP and all subsequent doses should be inhaled approximately 12 hours after the first dose.
 
Visit 2, Week 2: Spirometry will be obtained. Blood will be drawn for safety profiles and trough levels of CsA. A pregnancy test will be performed for all females of childbearing

	
potential. A physical exam, including vital signs, will be performed. The CGI Questionnaire will be administered. The SF-36 Quality of Life Questionnaire will be administered. A dose of the IMP will be administered under observation. Patients will bring used and unused vials of the IMP for availability check.
 
Visit 3, Week 4: During on-site visits, spirometry will be obtained. Blood will be drawn for safety profiles and trough levels of CsA. A pregnancy test will be performed for all females of childbearing potential. A physical exam, including vital signs, will be performed. The CGI Questionnaire will be administered. The SF-36 Quality of Life Questionnaire will be administered. An Investigator's Tolerability Assessment will be performed. A dose of the IMP will be administered under observation during on-site visits. Patients will bring used and unused vials of the IMP for availability check at on-site visits.
 
Visit 4, Week 8: During on-site visits, spirometry will be obtained. Blood will be drawn for CsA trough level and safety parameters. A pregnancy test will be performed for all females of childbearing potential. A physical exam, including vital signs, will be performed. The CGI Questionnaire will be administered. The SF-36 Quality of Life Questionnaire will be administered. A dose of the IMP will be administered under observation during on-site visits. Patients will bring used and unused vials of the IMP for availability check at on-site visits.
 
Visit 5, Week 12 (EoT): Spirometry will be obtained. Blood will be drawn for CsA trough level and safety parameters. A pregnancy test will be performed for all females of childbearing potential. A physical exam, including vital signs, will be performed. The CGI Questionnaire will be administered. The SF-36 Quality of Life Questionnaire will be administered. An Investigator's tolerability assessment will be performed. Patients will return all used and unused vials of the IMP. Drug accountability will be performed. The L-CsA CCI will be returned.

--	---

	
Visit 6, Week 14 (EoS): Blood will be drawn for safety parameters. A pregnancy test will be performed for all females of childbearing potential. A physical exam, including vital signs, will be performed.
 
Safety and tolerability will be monitored by documentation of AEs throughout the study.
 
Every effort will be made to have all planned and unscheduled visits at the study site. Mandatory on site visits are Screening and Visit 1, Visit 2 and Visit 5.
 
However, if one of the visits V3, V4 and V6 cannot be performed at site due to COVID-19, remote visits (e.g. by telephone) are possible. COVID-19 related Adverse Events will be reported as SAEs.

Data Monitoring Committee:	
A Data Monitoring Committee (DMC) is established to monitor the safety of IMP. The DMC will monitor safety by evaluating the safety analyses generated by the independent statistician during the course of the clinical trial. Details of the safety analyses will be included in the DMC Charter.
 
The DMC will evaluate treatment groups for possible trends in AEs, determine whether the basic protocol assumptions remain valid, evaluate whether the overall integrity, scientific merit and conduct of the clinical trial remain acceptable, and make recommendations to the Sponsor.

Statistical Considerations:	
Exploratory statistical analyses will be performed using methods of descriptive data analysis.
 
Analysis of safety: MedDRA coded, treatment emergent adverse events (TEAEs) will be tabulated at the Preferred Term (PT) and the System Organ Class (SOC) levels. Treatment group comparisons of the proportion of patients with TEAEs will be based on Wilson score confidence intervals. Pairwise group comparisons will be provided at the SOC level as well as for the events identified as local tolerability measures (cough, wheezing, bronchospasms, throat irritation, change in FEV₁), with separate analyses for all events with onset during the first 4 weeks of treatment and for events with onset at any time during randomized treatment. CGI scales will be analysed and compared between the treatment groups.
 
Analysis of efficacy: Spirometric variables and SF-36 scales will be analyzed and compared between the treatment groups using mixed models for repeated measures (MMRM).
 
Pharmacokinetic measures: The statistical analysis will be carried out based on a multiplicative model for AUC_{0-4 h} and C_{max} values, while t_{max} and trough levels will be evaluated on the basis of an

	
additive model. Analyses of variance will be performed to compare the treatment groups.
 
Sample size determination: The sample size for the study was established based on considerations of feasibility rather than on power calculations. A total of 24 patients (3 arms x 8 patients each) are planned to be randomized.

--	---

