8.5 Stopping Rules and Discontinuation Criteria

8.5.1 Patient Level

Regular termination of clinical trial participation:

The investigational treatment will be terminated after 12 weeks (End of Treatment [EoT]). The treatment period will be followed by a 2-week follow-up period (End of Study [EoS]). Any patients with ongoing AEs and SAEs will be followed-up until recovery or stabilization of the AE/SAE.

Premature termination of clinical trial participation:

- Patients may discontinue participation in the clinical trial at any time by revoking their informed consent.
- The Investigator may withdraw a patient at any time if it is in the best interest of the patient based upon clinical assessments.
- Patient is lost to follow-up
- Pregnancy (the patient will be followed via the sponsor's safety department)
- Termination of the clinical trial as a whole by Zambon SpA as defined in [section 8.5.3](#).

If the participant fails to return for clinical follow-up, the patient will be contacted by telephone or a letter will be sent requesting a clinic visit (EoS), and the reason for non-compliance will be documented. The final visit will encompass the assessments listed under EoS Visit (Visit 6; [Section 13.2.5](#)). Additionally, used and unused IMP and inhalation device will be retrieved, if applicable. Zambon SpA will be notified that the patient has terminated clinical trial participation.

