8.6 Investigational Medicinal Product: Supply and Accountability

Each Investigator is responsible for ensuring that deliveries of IMP vials and boxes, L-CsA CCI and other clinical trial materials are correctly received and recorded, that these are handled and stored safely in a locked and temperature controlled storage place with access for authorised study staff only and that they are used in accordance with this protocol. In addition, the Investigator will monitor each patient's treatment compliance by counting the used/unused drug vials at each visit.

For the purpose of this trial patients will be regarded as compliant if no more than 45 vials of IMP over the entire treatment period of 12 weeks are returned as unused – this corresponds to approximately 75% treatment compliance. The reason for non-compliance shall be documented according on the respective eCRF.

Unused IMP vials, ampoules, boxes, and L-CsA CCI must be returned or destroyed on-site after accountability has been completed and destruction is approved by Zambon SpA. A list of IMP, L-CsA CCI, and other materials received, used, returned, or destroyed must be prepared, completed and signed by the Investigator; any discrepancies must be accounted for.

COVID-19 specific consideration: the patients will be supplied during V1 with the full amount of study medication needed, to cover the total treatment period of 12 weeks. Patient has to bring all study medication back to the site at EoT Visit V5 for Drug Accountability.

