12.1.6.3 Cyclosporine A Whole Blood Trough Levels

A whole blood sample for the determination of cyclosporine A trough level will be collected at Visit 2 to Visit 5 at each on-site visit. The sample should be collected 15 minutes before inhalation. The trough levels of CsA at visit 2 to 5 will be analysis will be performed in a central laboratory (CCI [REDACTED]).

All sites will be provided with specific Laboratory Kits for collecting the PK blood samples. Blood should be collected into the respective pre-labelled K2-EDTA Tubes and should be stored at -20°C immediately after collection until shipment to the central laboratory.

Instruction on handling, processing, storage and shipment are in detailed described in the Laboratory Manual for Pharmacokinetic Blood Sampling.

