13.2.3 Visit 2 through Visit 5 / EoT

- Physical examination
- Vital signs
- Clinical laboratory tests
- Cyclosporine A whole blood trough levels (blood sample pre-dose)
- Urine/Serum pregnancy test
- Spirometry
- IMP Administration
- Concomitant medications/therapies
- AEs
- CGI (Items 1-3)
- SF-36 questionnaire
- Local IMP tolerability
- Drug Accountability by vial count (Visit 5 only)
- Check IMP supplies of patient

13.2.4 Visit 3 and Visit 5

- In addition to the assessments described in section 13.2.3, the clinical investigator will perform an Investigator's Tolerability Assessment assessed by means of a five-point verbal rating scale with the response options 'very good', 'good', 'satisfactory', 'moderate', and 'poor'.

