## 8 INVESTIGATIONAL PLAN

### 8.1 Trial Design

This is a Phase IIa, prospective, multicenter, randomized, single-blind, placebo-controlled clinical trial of L-CsA for the treatment of BOS in adults with confirmed BOS following allo-HSCT. Patients will receive either L-CsA 5 mg or L-CsA 10 mg or placebo via the **CCI** [REDACTED] System twice daily in addition to SoC treatment, for a period of 12 weeks (see Table 1).

A total of the following visits will be performed during the clinical trial:

- Screening
- Week 0 (Randomization/Baseline) [Visit 1]
- Week 2 [Visit 2]
- Week 4 [Visit 3]
- Week 8 [Visit 4]
- Week 12 (End of Treatment (EoT) [Visit 5]
- Week 14 (End of Study (EoS) [Visit 6]

After informed consent has been obtained, a Screening Visit will be carried out in order to determine the eligibility for randomized treatment. At the Baseline Visit (V1, randomization visit), inclusion and exclusion criteria will be re-confirmed and baseline spirometry performed. During the 12-week treatment period, interim visits are scheduled at weeks 2, 4, and 8 (V2 – V4). Visit 5 (End of Treatment, EoT) is scheduled to occur 12 weeks after Visit 1. Visit 6 (End of Study, EoS) is a safety follow-up visit performed 2 weeks after Visit 5/EoT.

However, if one of the visits V3, V4 and V6 cannot be performed at site due to COVID-19, remote visits (e.g., by telephone) are possible. COVID-19 related Adverse Events will be reported as SAEs.

COVID-19 specific consideration: the patients will be supplied during V1 with the full amount of study medication needed, to cover the total treatment period of 12 weeks. Patient has to bring all study medication back to the site at EoT Visit V5 for Drug Accountability.

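### The 12-week treatment maximum is not reconciled with a Visit 5 that may fall up to 7 days later, so some Week 12 troughs and lung-function values may be taken off drug and pooled with on-drug values

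*Protocol*

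**What the plan says.** **Length of treatment.** The synopsis (Treatment Regimen) and Protocol 8.3.2.2 give "L-CsA 10 mg/2.5 mL bid for a maximum of 12 weeks", with the same limit for the other two arms. Protocol 8.2 and 10 also limit dosing to 12 weeks. Protocol 8.5.1 states: "The investigational treatment will be terminated after 12 weeks (End of Treatment [EoT".

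**Timing of Visit 5.** SAP 8.1 states: "Visit 5 (End of Treatment, EoT) is scheduled to occur 12 weeks after Visit 1". The schedules in Protocol 13 and SAP Table 1 allow 7 days either side. The label EoT is thus used both for the 12-week limit and for a visit that may come a week later.

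**What happens at Visit 5.**
- Protocol 12.1.6.3: the "trough level will be collected at Visit 2 to Visit 5 at each on-site visit", 15 minutes before inhalation. Footnote 5 of the schedule says the same.
- Protocol 13.2.3, covering Visits 2 to 5, lists "Cyclosporine A whole blood trough levels (blood sample pre-dose" and also lists IMP administration.
- The synopsis (Mode of Administration) says: "At every visit, one dose administered via inhalation will be monitored by the clinical trial center personnel". Protocol 8.3.2.3 likewise asks for an observed dose at visits after the first.
- The synopsis paragraph for Visit 5 says "Blood will be drawn for CsA trough level and safety parameters" and has vials and device returned. It lists no observed dose, whereas the paragraphs for Visits 2, 3 and 4 each do.

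**Supply.** Protocol 8.6 has patients given, at Visit 1, "the full amount of study medication needed, to cover the total treatment period of 12 weeks". The number of vials is not stated.

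**Analysis.** SAP 14.2 analyses PK, Week 12 trough included, as a valid-case analysis of all FAS patients. SAP 15.1 models spirometry at the scheduled visits. Neither refers to time since last dose.

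**The concern.** A completer whose Visit 5 is late cannot satisfy every rule. If dosing stops at 12 weeks, the visit falls after treatment and a sample called pre-dose precedes no scheduled dose. If dosing runs on to the visit, the stated maximum is exceeded. Sites could resolve this differently, and the plan would not show which way each patient went.

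What is at stake is how the Week 12 data are interpreted: the trough, supervised local tolerability, the investigator's tolerability rating, CGI, SF-36 and spirometry. These are secondary or exploratory outcomes. The trough is the most exposed, because its meaning depends entirely on the interval since the last dose. Supervised local tolerability depends on an inhalation taking place: Protocol 12.1.5 provides an hour of observation after it, and SAP 13.1 counts only events that appear within an hour of an inhalation.

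**Working it through.** **Step 1. The plan's own supply figure.** Protocol 8.6 equates 45 unused vials with approximately 75% compliance. Compliance = 1 − 45/N.
- N = 12 × 7 × 2 = 168 vials: 1 − 45/168 = 73.2%.
- N = 180, three of the 60-vial boxes in Protocol 8.4.1: 1 − 45/180 = 75.0%.

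Both fit the stated figure, so the documents do not settle how many vials are dispensed.

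**Step 2. Calendar.** Visit 1 is Day 1. Twelve weeks is 84 days, or 168 doses. Nominal Visit 5 is Day 1 + 84 = Day 85, and the window is Day 78 to Day 92. Assumptions: first dose on the morning of Day 1, full adherence, and a morning Visit 5.

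**Step 3. Reading A: dosing stops on the evening of Day 84.** For visits from Day 85 on, hours since last dose = (visit day − 84) × 24 − 12, and dose slots passed without a dose = (visit day − 85) × 2.

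| Visit 5 on | Hours since last dose | Slots without a dose |
|---|---|---|
| Day 85 (nominal) | 12 | 0 |
| Day 86 (+1) | 36 | 2 |
| Day 88 (+3) | 84 | 6 |
| Day 90 (+5) | 132 | 10 |
| Day 92 (+7) | 180 (7.5 days) | 14 |

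Protocol 9.3.1 says IMP should not be resumed after 10 or more consecutive missed doses. If these slots count as missed, which the text does not say, an inhalation at Visit 5 conflicts with that rule from Day 90.

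**Step 4. Reading B: dosing continues to Visit 5.** The interval stays at 12 hours while supply lasts, and treatment exceeds 12 weeks by up to 92 − 85 = 7 days. Vials needed, including one at the visit, = (visit day − 1) × 2 + 1. This gives 181 on Day 91 and 183 on Day 92. If 180 vials are dispensed (assumption), a fully adherent patient has none left for Visit 5 on those two days, and the interval on Day 92 becomes 36 hours.

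**Step 5. Effect on the trough under Reading A.** The documents give no half-life, so I assume 6 to 24 hours. The inhaled contribution relative to a 12-hour trough is 2^(−(hours − 12)/half-life).

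| Half-life (assumed) | Visit at +1 day | Visit at +7 days |
|---|---|---|
| 6 h | 2^(−24/6) = 6% | 2^(−168/6), under 0.000001% |
| 12 h | 2^(−24/12) = 25% | 2^(−168/12) = 0.006% |
| 24 h | 2^(−24/24) = 50% | 2^(−168/24) = 0.8% |

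This concerns the inhaled contribution only; Protocol 10.1.2 permits systemic cyclosporine.

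**Step 6. Effect on an arm summary.** SAP 14.2 reports arithmetic and geometric means. As an illustration, take 8 patients with equal 12-hour levels, no systemic cyclosporine and no assay limit, and let one be sampled at +7 days off drug. The arithmetic mean falls by about 1/8 = 12.5%. The geometric mean is multiplied by 2^(−168/(8 × half-life)) = 2^(−21/half-life). That is 0.55 at 24 h, 0.30 at 12 h and 0.09 at 6 h, a fall of 45% to 91%.

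**The case against.** The best reply is that the documents point to dosing up to Visit 5. The schedule places V5/EoT inside the treatment period, vials and device come back at that visit, the trough is defined by an inhalation that follows it, and SAP 16.2 measures compliance from baseline to EoT. On that view nobody is off drug by schedule while supply lasts, and the remaining fault is a nominal 12 weeks that ignores a routine visit window. This is a fair reading, but no section states it, and the maximum in the synopsis, 8.3.2.2 and 8.5.1 says otherwise.

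A reader might also infer more than the documents support:
- **That Week 12 data certainly mix on-drug and off-drug completers.** This needs both a stop at Day 84 and a late visit.
- **That the synopsis rules out a dose at Visit 5.** It does not. Its every-visit rule includes Visit 5, and the Visit 5 paragraph omits the dose without prohibiting it.
- **That the maximum is breached even on the nominal day, because that dose is number 169.** With 12-hourly dosing the 169th dose falls 168 × 12 h = 84 days after the first, so this is only a matter of how the end points are counted.
- **That supply will run out.** The number of vials is not stated; Step 4 rests on an assumption.
- **That Visit 5 is the only supervised inhalation after Week 2.** This holds only if Visits 3 and 4 are both remote because of COVID-19. Local events between visits are also solicited (Protocol 12.1.5).

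Two further points against the concern stand. The between-group ANOVA in SAP 14.2 covers only AUC and Cmax, so the Week 12 trough is one of four descriptive time points. Patients who stop IMP keep attending visits (Protocol 9.3.1), so some off-drug Week 12 data are intended. The second point also supports recording time since last dose.

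**Conclusion.** The concern holds as an unreconciled conflict, not as a demonstrated bias. A completer seen 1 to 7 days after the nominal day either exceeds the stated maximum by up to 7 days (14 doses), or has Week 12 measures taken 36 to 180 hours after the last dose. In the second case the sample is not a trough at any half-life in the assumed 6 to 24 hour range. Week 12 data may therefore mix on-drug and off-drug values, and the SAP as written would pool them.

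The intervals assume a morning Visit 5 and full adherence up to the stop. How often Visit 5 will be late is unknown, and the documents give nothing from which to size the effect of a week off drug on FEV1, CGI or the tolerability rating. The 4-week primary assessment and visits from Day 78 to Day 85 are not affected in this way. The outcomes concerned are secondary and exploratory, so this is an inexpensive correction that should be made, not a threat to the trial's main conclusion.

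**What to change.** **Protocol and SAP text.** Reconcile the synopsis (Mode of Administration, Treatment Regimen, Visit 5 paragraph), Protocol 8.2, 8.3.2.2, 8.3.2.3, 8.5.1, 10, 13 (schedule and footnote 5) and 13.2.3, and SAP 8.1. They should agree on when dosing ends relative to Visit 5 and on whether a supervised dose is inhaled there. The visit window and the number of vials dispensed should then match. Which rule applies is for the sponsor to decide; this review does not choose one.

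**SAP 14.2.** Derive hours from last dose to the Week 12 sample, using the administration dates and times already to be listed under SAP 16.2. Summarise as trough only samples taken about one dosing interval after the last dose, with the tolerance fixed before database lock. List the other samples separately with their interval.

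**SAP 15.1.** Flag Week 12 spirometry values taken off drug, and keep all values in the main FAS analysis.

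**Cost.** Wording changes, one derived variable, and possibly a few fewer Week 12 trough values in the summary. No new eCRF field, visit or patient is needed, provided the administration times are captured as SAP 16.2 plans.
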